9.3.4 TABULATION OF INDIVIDUAL PARTICIPANT DATA

All clinical, behavioral and neuroimaging measures will be listed by time point when applicable.

9.3.5 EXPLORATORY ANALYSES

Linear regression models will be built to test whether change in cognitive control indices (behavioral, brain activations and functional connectivity) will associate with change on clinical outcomes (PARS scores). The standardized parameter estimates in each model will be examined. Secondary logistic regression will be conducted on CBT responder status.

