Eighteen RMT subjects in the parent study will be recruited to our CBT+CCT group, and thirty-six age- and gender-matched CBT subjects in the parent study will be recruited to our CBT control group. The proposed study may add:

- 1) For all fifty-four subjects recruited from parent study:
 - a. NIH Toolbox and/or Millisecond behavioral assessment before and after the CBT course of therapy as well as once before the RMT course of treatment and once at about 3 weeks of CBT and another time if completing the fMRI following 4 weeks of at home CCT for the CBT+CCT group
 - b. BRIEF2 questionnaire before, after, and at about week 3 of the CBT course of treatment, as well as once before the RMT course of treatment and at the fMRI following 4 weeks of at home CCT for the CBT+CCT group
 - c. Clinical assessment of anxiety at week 3 of CBT treatment.
- 2) For patients originally randomized to RMT in the parent study who wish to enroll in the current study during their Optional CBT participation:
 - a. augmentation of the CBT offered by the parent R01 study with CCT games delivered prior to each CBT session (CBT+CCT) along with a brief survey (the Self-Assessment Manikin) they may be asked to complete before and after CCT
 - b. fMRI following 4 weeks of at home CCT, and fMRI following CBT+CCT completion
 - c. Clinical measures and assessments before and throughout the course of CBT treatment
 - d. at home CCT (~30 min/day), 5x per week, for up to 4 weeks, for up to two weeks before starting CBT and for up to 4 weeks after starting CBT, along with a brief survey (the Self-Assessment Manikin) they may complete before and after CCT

Data analyses will compare pre- and post-CBT data from the parent study with pre- and post-CBT+CCT data collected for the proposed study. These data will include NIH Toolbox and/or Millisecond measures of behavioral capacity for cognitive control; multi-modal assessment of TCN with fMRI, resting state and DTI; and, detailed assessment of anxiety symptoms using both clinician-interview and self-report. Pre- to post-therapy change in anxiety severity (clinician-measured) will serve as the primary outcome variable; regression analyses will be used to test for associations of anxiety change with changes in brain-behavioral indices of cognitive control following CBT compared to CBT+CCT. To increase clinical relevance of study results, analyses will also consider responder status, a common end point for clinical trials.

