4.2 SCIENTIFIC RATIONALE FOR STUDY DESIGN

We hypothesize that CCT, delivered immediately prior to CBT sessions, will exercise task-control network and thereby facilitate the receipt of CBT. So in the control group, age- and gender-matched anxious youth received CBT only; their behavioral, brain and clinical data will serve as comparison, to evaluate whether CCT will augment the CBT effect.

The aims of this project are to:

- (1) Examine whether CBT+CCT will further engage the TCN. We hypothesize that (a) both groups will have increased activation and functional connectivity in task-control network after therapy vs. before therapy; however, (b) the increase will be greater in CBT+CCT vs. CBT only group.
- (2) Examine whether CBT+CCT will further improve cognitive control capacity. We hypothesize that (a) both groups will have improved behavioral performance on the conflict interference task and tasks testing cognitive control capacity included in the NIH Toolbox; however, (b) these effects will be greater in CBT+CCT vs. CBT group.
- (3) Examine whether CCT will augment the CBT outcome. We hypothesize that relative to CBT group, anxiety severity will be reduced more and treatment response rate will be higher in CBT+CCT group.
- (4) Explore the associations between changes in TCN, behavioral and CBT outcome. We hypothesize that increased TCN activation and functional connectivity, and improved behavioral performance on cognitive control tests will correlate with better treatment outcome in both groups.

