9 STATISTICAL CONSIDERATIONS

9.1 STATISTICAL HYPOTHESES

- Primary Endpoint(s): Change in Brain activation and connectivity in the task-control network (TCN)

We hypothesize that **(a)** both groups will have increased activation and functional connectivity in task-control network after therapy vs. before therapy; however, **(b)** the increase will be greater in CBT+CCT vs. CBT only group. Baseline and week 12 assessment will evaluate pre- to post-CBT changes in brain activation and function connectivity in the task-control network including fronto-parietal and cingulo-opercular regions mediating cognitive control. Functional activation and connectivity of these brain regions are assessed using a conflict interference computer task performed during MRI scanning.

- Secondary Endpoint(s):
 - (1) Change in behavioral performance on the conflict interference task and tasks testing cognitive control capacity included in the NIH Toolbox: We hypothesize that **(a)** both groups will have improved behavioral performance on the conflict interference task and tasks testing cognitive control capacity included in the NIH Toolbox; however, **(b)** these effects will be greater in CBT+CCT vs. CBT group. This will be evaluated using two measures of the same construct at baseline and week 12. Pre- to post-CBT changes in the behavioral performance in a conflict interference task will be collected, as well as composite score from tasks included in the NIH toolbox.
 - (2) Change in Pediatric Anxiety Rating Score (PARS): We hypothesize that relative to CBT group, anxiety severity will be reduced more and treatment response rate will be higher in CBT+CCT group. This will be evaluated at baseline and week 12 through the PARS, a 50 question interview-based tool used to assess for the presence and severity of anxiety symptoms in children and adolescents utilizing parental and youth input to guide clinician ratings. The total scores on this scale range from 0 to 30, with scores above 13 indicating clinically meaningful anxiety.

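### Section 9.3.5 states the exploratory change-on-change regressions without a group term, so they can mix between-group with within-group association

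*Combined protocol and SAP*

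**What the plan says.** Section 9.3.5 gives the model in one sentence: "Linear regression models will be built to test whether change in cognitive control indices", whether behavioural or neural, is associated with change in PARS score. What is read from it, and the binary counterpart, follow: "The standardized parameter estimates in each model will be examined. Secondary logistic regression will be conducted on CBT responder status". No group factor, interaction, by-group fit or covariate is named.

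Two other places give group a role in this analysis. Section 4.1 says the regressions relate anxiety change to "changes in brain-behavioral indices of cognitive control following CBT compared to CBT+CCT". Aim 4 in section 4.2 expects that the brain and behavioural improvements "will correlate with better treatment outcome in both groups".

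Sections 9.3.2 and 9.3.3, by contrast, write out the between-subject factor (CBT versus CBT+CCT) for the repeated-measures ANOVAs on the primary endpoint and on behavioural performance.

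On how group relates to the two variables, section 9.1 predicts for network activation and connectivity that "the increase will be greater in CBT+CCT vs. CBT only group", and also predicts a larger PARS reduction with CBT+CCT. Section 6.3 states that this pilot is not randomised. CBT+CCT participants come from the parent study's RMT arm and controls from its CBT arm.

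**The concern.** If group moves both the predictor (index change) and the outcome (PARS change), a single slope fitted across all participants combines two things: how the changes go together within a treatment group, and how far apart the group means lie. Aim 4 concerns only the first. On the trial's own hypotheses the second is not zero.

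Nor does it require CCT to work as hoped. Before their CBT, the CBT+CCT participants have been through a course of RMT, and under section 8.2 their PARS may be repeated before at-home CCT only if more than about six weeks have passed since the RMT week 12 score. PARS change could therefore differ between groups for reasons unrelated to CCT, in either direction. If group shifts the two scores in opposite directions, the same model can hide a real within-group association.

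At stake is the reading of the mechanism analysis, namely whether engaging the task-control network goes with benefit from CBT. Section 9.2 says the pilot is meant to supply effect sizes for a later application. A standardised coefficient that mixes the two sources is a poor input to that.

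**Working it through.** **Inputs from the documents.** Enrolment of 36 CBT and 18 CBT+CCT, therapy retention of 96.2%, usable-motion rate of 89%, and expected usable pre/post data on 32 and 14 (all section 5). Two-tailed 5% level (section 9.3.1). No effect sizes or power figures (section 9.2).

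**The plan's own figure.** 36 × 0.962 × 0.89 = 30.8 (stated 32). 18 × 0.962 × 0.89 = 15.4 (stated 14). The total is 46.2 (stated 46). Each arm is within two participants, so the stated 32 and 14 are used.

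**Assumptions.** Change scores are normal with equal within-group SDs, and both are oriented so that positive means improvement. Group differences d1 (index change) and d2 (PARS change) are in within-group SD units. All d values are assumed and shown as a range.

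**Pooled correlation when the within-group correlation is zero.** With pq = (14/46)(32/46) = 0.2117,

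r = pq·d1·d2 / √[(1 + pq·d1²)(1 + pq·d2²)].

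For d1 = d2 = 0.8: 0.2117 × 0.64 = 0.1355, and 0.1355/1.1355 = 0.119.

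**Rejection rate of the two-sided 5% slope test** (40,000 simulated data sets of 46):

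| d1 = d2 | pooled r | no group term | with group term |
|---|---|---|---|
| 0.3 | 0.02 | 5% | 5% |
| 0.5 | 0.05 | 6% | 5% |
| 0.8 | 0.12 | 12% | 5% |
| 1.0 | 0.17 | 22% | 5% |
| 1.2 | 0.23 | 36% | 5% |

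Unequal shifts give less: 8% at 0.8 and 0.5, 6% at 0.8 and 0.3, and 5% (no inflation) at 0.8 and 0.

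The 32 and 14 include losses to scan motion, so more data may be usable for the behavioural indices. With the full 36 and 18 the rates without a group term are 6.7%, 14.8%, 26.3% and 44.5% at 0.5, 0.8, 1.0 and 1.2 SD.

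**Masking.** Take an assumed within-group correlation of 0.4 at 32 and 14. Power with a group term is 79%. Without it, power is 62% if group shifts the two scores by +0.5 and −0.5 SD, and about 49% at +0.8 and −0.5.

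**Precision in the smaller arm.** With n = 14, an observed correlation of 0.3 has a 95% CI of tanh(0.3095 ± 1.96/√11) = −0.27 to 0.72. It would have to exceed about 0.53 in absolute size to reach p < 0.05.

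The logistic model was not simulated. The reasoning about group carries over to it, but the percentages do not.

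**The case against.** The strongest reply is that section 9.3.5 is brief rather than wrong. It never says that the groups are pooled and does not list the full right-hand side of any model. Section 4.1 gives group a role, and Aim 4 would fit by-group models. That stands in part. A reader might infer that the plan deliberately excludes group, and the documents do not support this. What they show is that the statistical section fails to carry through a comparison announced in the design section, although it spells out the group factor for the ANOVAs.

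Second, inflation is material only if group shifts both scores by a large amount. CCT is an add-on to an active therapy, and both groups are expected to improve. This stands. A reader might infer that a false association will arise. The documents give no effect size from which to say so, and at 0.5 SD or below the inflation is negligible.

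Third, section 3 lists the objective as tertiary/exploratory, and the tests of CCT itself in 9.3.2 and 9.3.3 compare the groups directly. This also stands and limits the consequence. No confirmatory claim depends on 9.3.5.

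Fourth, a full interaction model would have little power. With 14 and 32, power is about 30% for within-group slopes of 0.5 versus 0. This argues against making an interaction test the basis for Aim 4. It does not argue against a group main effect.

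**Conclusion.** The point holds as a mismatch with a cheap remedy. As written, 9.3.5 cannot separate within-group from between-group association and cannot deliver either the comparison in 4.1 or the both-groups statement in Aim 4. That much needs no assumed effect size.

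The numerical consequence is conditional. False-positive rates run from about 5% at 0.3 SD to 36% at 1.2 SD on both scores, given 14 against 32, zero within-group correlation and normal change scores with equal variances. There is no inflation if group shifts only one score. Opposing shifts cost power instead.

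A reader might go further and conclude that the plan needs a formal interaction test, adjustment for pre-therapy PARS, or a four-predictor logistic model. Neither the documents nor the calculations support requiring these. The group main effect alone restores the 5% level in the linear model, baseline PARS is a separate question, and about 14 participants in one arm will not support a larger logistic model well.

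**What to change.** In section 9.3.5, add group (CBT versus CBT+CCT) as a main effect to both the linear and the logistic models, and state that the Aim 4 conclusion rests on the group-adjusted slope. For the linear model, also report each group's slope and the difference in slopes with 95% confidence intervals. Label these as descriptive and note that they will be imprecise with about 14 in CBT+CCT. This brings 9.3.5 into line with 4.1 and Aim 4.

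The cost is one sentence of text and one degree of freedom in the main model. No new data are needed, and the analysis keeps its exploratory label.

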10 SUPPORTING DOCUMENTATION AND OPERATIONAL CONSIDERATIONS

10.1 REGULATORY, ETHICAL, AND STUDY OVERSIGHT CONSIDERATIONS

10.1.1 INFORMED CONSENT PROCESS

10.1.1.1 CONSENT/ASSENT AND OTHER INFORMATIONAL DOCUMENTS PROVIDED TO PARTICIPANTS

Consent forms describing in detail the study intervention, study procedures, and risks will be given to the participant and written or electronic documentation of informed consent will be completed prior to starting the study intervention.

10.1.1.2 CONSENT PROCEDURES AND DOCUMENTATION

The protocol will begin by having the subject (or their parent[s] for adolescent subjects) provide assent and written informed consent. In the case that social distancing policies prohibit this type of in-person study activity (e.g., during COVID-19), informed consent will be obtained at the beginning of a remote visit. This remote visit will include a review of an oral assent script, assent from the minor subject, and signed electronic consent from the subject and their parent/guardian. Electronic informed consent signatures will be collected using SignNow. All procedures will adhere to the IRBMED Guidance for use of SignNow for Electronic Informed Consent Procedures. Informed consent is a process that is initiated prior to the individual's agreeing to participate in the study and continues throughout the individual's study participation. Extensive discussion of risks and possible benefits of this therapy will be provided to the subject/parents. Consent forms (written in non-technical language, understandable by the youngest subject to be enrolled in the study) describing in detail the study interventions/products, study procedures, and risks will be given to the subject/parent. Participants may also be presented with a visual timeline of the tasks that may be involved in participating in this study, during the consenting process or at another time during the study, to aid their understanding of the process. Upon reviewing the document, one of the investigators (or their designee) will explain the research study to the subject/parent and answer any questions that may arise. The subject/parent will sign the informed consent document prior to any procedures being done specifically for the study. Adolescent subjects will be asked to sign in the assent box on the main consent. The subjects may withdraw consent at any time throughout the course of the trial. The rights and welfare of the subjects will be protected by emphasizing that the quality of their medical care will not be adversely affected if they decline to participate in this study. As some of the patients may also be treated by members of the study team, we will take special care to emphasize the voluntary nature of participation. NOTE: older teens may become legal adults (i.e., reach the age of 18 years) during the course of the study. If the teen is still actively involved in the study (i.e., data collection ongoing), then a new consent form, signed by the teen, will be obtained. However, if the teen reaches 18 years of age *after* their data collection has been completed, we will *not* re-contact to re-consent. This approach is intended to avoid burdening study participants and their parents.

10.1.2 STUDY DISCONTINUATION AND CLOSURE

This study may be temporarily suspended or prematurely terminated if there is sufficient reasonable cause. Written notification, documenting the reason for study suspension or termination, will be provided by the suspending or terminating party to study participants, funding agency, and regulatory authorities. If the

study is prematurely terminated or suspended, the Principal Investigator (PI) will promptly inform study participants, the Institutional Review Board (IRB), and sponsor/funding agency and will provide the reason(s) for the termination or suspension. Study participants will be contacted, as applicable, and be informed of changes to study visit schedule.

Circumstances that may warrant termination or suspension include, but are not limited to:

- Determination of unexpected, significant, or unacceptable risk to participants
- Demonstration of efficacy that would warrant stopping
- Insufficient compliance to protocol requirements
- Data that are not sufficiently complete and/or evaluable
- Determination that the primary endpoint has been met
- Determination of futility

The study may resume once concerns about safety, protocol compliance, and data quality are addressed, and satisfy the funding agency, sponsor, IRB, or other relevant regulatory or oversight body.

10.1.3 CONFIDENTIALITY AND PRIVACY

Participant confidentiality and privacy is strictly held in trust by investigator, research staff, and the sponsor(s) and funding agency. This confidentiality is extended to the data being collected as part of this study. Data that could be used to identify a specific study participant will be held in strict confidence within the research team. No personally-identifiable information from the study will be released to any unauthorized third party without prior written approval of the sponsor/funding agency.

All research activities will be conducted in as private a setting as possible.

The study monitor, other authorized representatives of the sponsor or funding agency, representatives of the Institutional Review Board (IRB), regulatory agencies or representatives from companies or organizations supplying the product, may inspect all documents and records required to be maintained by the investigator, including but not limited to, medical records (office, clinic, or hospital) and pharmacy records for the participants in this study. Research team will permit access to such records.

The study participant's contact information will be securely stored for internal use during the study. At the end of the study, all records will continue to be kept in a secure location for as long a period as dictated by the reviewing IRB, Institutional policies, or sponsor/funding agency requirements.

All paper and computer research records will be identified by subject ID number rather than name or other personally identifying information. Paper records are stored in a double-locked environment to which only authorized study team members have access. The link between subject ID and subject name will be kept in a separate password protected database. Consent documents and any other forms with identifying information will be maintained separately from research data files (identified by subject ID only).

Measures Taken to Ensure Confidentiality of Data Shared per the NIH Data Sharing Policies

It is NIH policy that the results and accomplishments of the activities that it funds should be made available to the public (see <https://grants.nih.gov/policy/sharing.htm>). The PI will ensure all mechanisms used to share data will include proper plans and safeguards for the protection of privacy, confidentiality, and security for data dissemination and reuse (e.g., all data will be thoroughly de-identified and will not be

traceable to a specific study participant). Plans for archiving and long-term preservation of the data will be implemented, as appropriate.

Certificate of Confidentiality

To further protect the privacy of study participants, the Secretary, Health and Human Services (HHS), has issued a Certificate of Confidentiality (CoC) to all researchers engaged in biomedical, behavioral, clinical or other human subjects research funded wholly or in part by the federal government. Recipients of NIH funding for human subjects research are required to protect identifiable research information from forced disclosure per the terms of the NIH Policy (see <https://humansubjects.nih.gov/coc/index>). As set forth in 45 CFR Part 75.303(a) and NIHGPS Chapter 8.3, recipients conducting NIH-supported research covered by this Policy are required to establish and maintain effective internal controls (e.g., policies and procedures) that provide reasonable assurance that the award is managed in compliance with Federal statutes, regulations, and the terms and conditions of award. It is the NIH policy that investigators and others who have access to research records will not disclose identifying information except when the participant consents or in certain instances when federal, state, or local law or regulation requires disclosure. NIH expects investigators to inform research participants of the protections and the limits to protections provided by a Certificate issued by this Policy.

The assessments in this protocol will ask participants about sensitive topics, such as mental illness, possible pregnancy and substance use. We will inform the consenting parents of minor participants at the beginning of the process that we will respect the confidentiality of our teenage participants. It is important for us to let teenage participants know that they can be honest about sensitive topics without fear of reprisal from their parents. However, participants will also be informed about limits to confidentiality. If we learn that a subject has potential to harm him or herself, or another individual, we will break confidentiality and take steps to prevent harm. Similarly, any evidence of potential child abuse will be reported to Child Protective Services. Since the assessment will occur along with clinical feedback to the minor participant and parents, we will need to discuss clinical situations that require an intervention, such as substance use disorders and substance use that interferes with treatment. If we become aware of imminent risk of harm to a parent, steps will be taken to ensure safety (e.g. referral to psychiatric emergency services or contacting appropriate authorities).

